Measuring the presence or absence of viral proteins (antigens), antigen tests may provide results diagnosing an active SARS-CoV-2 infection much faster than RT-PCR or equivalent tests. It has been argued that antigen tests may have a lower sensitivity than RT-PCR or equivalent RNA-based tests, and as a result they are much more likely to give false-negative results in individuals with lower amounts of virus. This may possibly make them unreliable in individuals with an asymptomatic course of the disease, in individuals in the first days of infection, and later than 5-7 days after onset of symptoms (SYNLAB press release, 22.09.2020).

2. Objective

The objective of this non-interventional study is to demonstrate that rapid antigen tests for SARS-CoV-2 (Abbott and Roche) provide fast results and perform equally well than RT-PCR, at least in symptomatic patients with high viral loads.

3. Study Design

The study will be performed in at the Corona Test Center Stuttgart Cannstadter Wasen operated by Dr. med. [name], Stuttgart, in close collaboration with the SYNLAB MVZ Leinfelden-Echterdingen GmbH. Approximately 2000 patients will be enrolled at after having signed the Informed Consent Form (ICF). Upon a scheduled study duration of eight weeks, we will be able to collect the required 2000 samples (50 patients per day).

One study visit is planned for data and blood collection (15,5 ml), antigen tests, RT-PCR, serological tests, basic laboratory tests to be communicated to participants, and ancillary blood tests (incriminated to be related to COVID-19 like inflammatory markers, and micronutrients and vitamins). These will be performed at the at the SYNLAB MVZ Leinfelden GmbH. Aliquots of the materials collected will be stored -20 degrees for control measurements and ancillary tests, maximally for one year after the last patient was enrolled into the study.

4. Rationale

In the past weeks, there has been much discussion about rapid antigen tests for SARS-CoV-2. The most recent generation of these tests, available from several different suppliers, are expected to perform well in patients with high viral loads. This is usually the case approximately 3-10 days after infection with the virus, when the person is contagious, and may be asymptomatic or in the first days of symptoms.

It is therefore hoped that rapid antigen tests can support diagnosis of COVID-19 in people who have the first symptoms. In the USA, some tests have received authorization for diagnostic testing in symptomatic individuals, within 5-7 days from the onset of symptoms (3).

5. Risks and benefits

Three nasopharyngeal swabs and one blood sample will be obtained from each of the participants. Antigen tests, RT-PCR and serological and ancillary laboratory tests are performed in this study.

Risks from nasopharyngeal swabs: The biggest risk is discomfort. Rarely - 1 in thousands — the person receiving the swab passes out from being super sensitive or gets a mild nosebleed.

Risks from blood draw: The risks of venipuncture include Minor bruising at the site where the blood is taken and hematoma (12 % approximately), with minor bruising being the most common reaction. Significant complications (defined as cellulitis, phlebitis, diaphoresis, hypotension, near syncope, syncope) are observed in approximately 3.5% of patients. The most frequent single significant complication is hypotension at a frequency occurred of approximately 2.6%. Syncope is seen in less than 1% of patients. Other serious local reactions such as cellulitis or phlebitis are very rare (Galena HJ, J. Fam. Pract. 1992 May;34(5):582-4). Blood sampling is therefore conducted in each of the study sites under the surveillance of a board licensed physician.

Benefits to public health: Point of care antigen testing is an integral component of the current national testing strategy serving for preventing of the spread of COVID 19
https://www.bundesgesundheitsministerium.de/fileadmin/Dateien/3_Downloads/C/Coronavirus/Nationale_Teststrategie_kurz_041220.pdf

There is, however, significant uncertainty as to the reliability of antigen testing in comparison to the gold standard of testing, rt-PCR. To the authors' knowledge a prospective, sufficiently sizeable and challengeable evaluation of antigen testing under

practice conditions has not been completed so far. The current study is intended to close this gap. Its results are urgently required and will have immediate impact on current recommendations for using antigen testing. In particular, it will demonstrate weaknesses and strengths of antigen testing and will allow to outweigh potential technical limitations of antigen testing compared to rt-PCR against the advantage of short-term availability of test results.

Further, the thorough recording of the clinical health status and the basic laboratory analysis performed in this study, it will be able to get further insights into clinical predictors for the susceptibility for COVID 19.

Benefits to the individual. Participants will benefit in two ways. Other than with rt-PCR, they will obtain the results of the antigen testing at once and on-site. In addition, offering two antigen tests simultaneously, the results of the point-of-care testing will be even more reliable than the result of a single test. Further, the participants are offered a free of charge basic laboratory health check including the following actionable health markers: basic blood cell count, C-reactive protein, HbA1c, cholesterol, triglycerides, LDL cholesterol, HDL cholesterol, gamma-glutamyl-transferase, creatinine along with formula-derived creatinine, vitamin D.

We conclude that benefits of this study to the healthcare system which is faced with the life-threatening and to the individual study participants clearly outweigh the minor and manageable risks.

6. Population

We will include approximately 2000 consecutive male and female patients aged 18 years or above attending the Corona Test Center Stuttgart Cannstatter Wasen, in whom RT-PCR testing for SARS-CoV-2 is medically indicated or requested.

6.1 Inclusion Criteria

Subjects eligible for inclusion in this study must meet the following criteria:

1. Signed informed consent must be obtained prior to study participation. The patient must be capable of understanding the nature, significance and implication of the trial.
2. Age 18 years or more

6.2 Exclusion criteria

1. Lack of informed consent
2. Inability to understand the nature, significance and implication of the trial.
3. Severe clinical conditions requiring emergency hospitalization
4. Children and adolescents under the age of 18 years

7. Informed consent procedures

Eligible subjects may only be included in the study after providing IRB/IEC-approved informed consent. Informed consent must be obtained before performing any study-specific procedures (Appendix 2).

8. Assessment schedule and assessments

Subject Table 8-1 Assessments

Assessments	Visit 1
Informed Consent Form, Appendices 1 and 2	X
Collection of demographic data and relevant Medical History (Appendix 3)	X
SARS-CoV-2 Rapid Antigen Test (Roche), Appendices 8 and 9	X
PANBIO Covid-19 Ag Rapid Test (Abbott), Appendices 5, 6 and 7	X
RT-PCR	X
Serological test (blood sample, 15,5 ml)	X
Ancillary testing	X

8.1 Demographics, Medical history, sampling

Patient demographic data and other characteristic data to be collected on all patients include sex, age, weight, height, relevant medical history, vital signs and symptoms characteristic of COVID-19 including precise time specifications for onset of symptoms (Appendix 3).

No information about medication will be collected.

Three independent nasopharyngeal swabs will be obtained following standard procedures

To avoid any bias due to the sequence of taking the nasopharyngeal swabs, we will randomly allocate the patients to three sampling groups

Group 1: RT-PCR – Antigen Test Roche – Antigen Test Abbott
Group 2: Antigen Test Roche – Antigen Test Abbott - RT-PCR
Group 3: Antigen Test Abbott - RT-PCR - Antigen Test Roche

The assignment of patients to each of these groups will be clearly specified on the case record forms. There will be two forms for each patient:

Form 1: Routine analysis request sheet as used by the collection point for patient identification which will be labelled with a bar code carrying the study number of a patient

Form 2: Study specific form containing a copy of the bar code with the study number, initials of the patient and the year of birth.

8.2 SARS-CoV-2 Rapid Antigen Test (Roche)

The SARS-CoV-2 Rapid Antigen Test is a rapid point of care chromatographic immunoassay for the qualitative detection of specific antigens of SARS-CoV-2 present in the human nasopharynx. (Appendices 8 and 9)

8.3 PANBIO Covid-19 Ag Rapid Test (Abbott)

Panbio COVID-19 Ag Rapid Test Device is an *in vitro* diagnostic rapid test for the qualitative detection of SARS-CoV-2 antigen (Ag) in human nasopharyngeal swab specimens. (Appendices 5; 6 and 7)

8.4 RT-PCR

RT-PCR evaluates the presence or absence of the SARS-CoV-2 genome in samples from nasopharyngeal and oropharyngeal swabs and will be conducted according to the protocols established at the SYNLAB MVZ Leinfelden GmbH.

8.5 Serological and ancillary testing

Blood samples (10 ml heparin plasma and 5.5 ml EDTA plasma) will be collected to detect the presence of antibodies (specific immune response) against SARS-CoV-2 antigenic proteins (e.g. Roche, Abbott). Specifically, all participants will be offered to receive the results for the following analytes in acknowledgment of their participation in the study: blood cell count, C-reactive protein, HbA1c, cholesterol, triglycerides, LDL cholesterol, HDL cholesterol, gamma-glutamyl-transferase, creatinine along with

formula-derived creatinine, vitamin D. Backup samples will be collected to determine ancillary parameters like inflammatory markers, and micronutrients and vitamins.

9. Observation Period

NIS schedule:

Start of the patient recruitment: February 1, 2021
End of the observation period: March 31, 2021
Final report: May 31, 2021

10. Data analysis and statistical methods

A database of the pseudonymized data and results will be generated. We hypothesize that each of the antigen tests has a sensitivity and specificity of 1.0 in relation to RT-PCR which will be considered as the reference test. A p value of less than 0.05 will be required to consider each of the two rapid tests equivalent to RT-PCR.

With the aid of *power calculations for chi-square tests* for two degrees of freedom, required type I error probability equal to 0.05, required (1-type II error probability) equal to 0.8 and required effect size equal to 0.1 (small effect size in the sense of (4)) we obtain a number of at least $N=964$ observations for consecutive testing of incoming patients in order to fulfill our requirements on significance and power to answer the first research question. Because of the expected number of around 10% positive out of 1000 cases, the assumption of a chi-square distribution is permissible.

We will also address the question whether different pre-test probabilities will affect the sensitivity of the antigen tests. We expect two major indication groups with different pre-test probabilities contributing approximately 90 percent of the rt-PCR positive samples: a) participants admitted for rt-PCR testing by a physician b) participants seeking for rt-PCR testing upon recommendation by health care authorities/contact persons. A total of approximately 200 rt-PCR samples will be required to detect a statistically significant difference between these two groups at a type 1 error of 0.05 and a statistical power of 0.80. To answer this second question, we will extend the study to 2000 participants.

11. Ethics

The study protocol will be submitted to the Ethics Committee the Medical Faculty Mannheim, University of Heidelberg and the study will not begin until written permission is obtained. The study will be conducted in accordance with German law, EU Clinical Trial regulations and the Declaration of Helsinki on the ethical principles of clinical research.

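### Section 10 declares each antigen test equivalent to RT-PCR on p < 0.05 without a null, table or margin, and no test that can be run from the text makes that p-value evidence of equivalence

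*Combined protocol and SAP*

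**What the plan says.** Section 2 sets out to demonstrate that the two rapid tests "provide fast results and perform equally well than RT-PCR", with a qualifier about symptomatic patients with high viral loads. Section 10 turns this into a hypothesis and a criterion: "We hypothesize that each of the antigen tests has a sensitivity and specificity of 1.0 in relation to RT-PCR", followed by "A p value of less than 0.05 will be required to consider each of the two rapid tests equivalent to RT-PCR".

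The only test named is in the sample-size paragraph of Section 10. It is a chi-square test with 2 degrees of freedom, type I error 0.05 and power 0.8: "required effect size equal to 0.1 (small effect size in the sense of (4)) we obtain a number of at least" 964 observations. With about 10% positives, the plan adds, "the assumption of a chi-square distribution is permissible". The extension to 2000 participants serves a second question, a comparison of sensitivity between two indication groups.

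No section labels a null hypothesis, names the contingency table, or gives an equivalence margin, a minimum performance or a confidence-interval rule.

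**The concern.** A p-value below 0.05 is evidence against a null. It supports equivalence only if the null is that the test falls short by at least a stated margin. Here no margin exists and the null is not identified.

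The 2 degrees of freedom do not settle the matter. An antigen-by-PCR table has 1. Two could come from comparing three methods, from a joint test of sensitivity and specificity, or, more remotely, from the swab-order groups of Section 8.1, where "we will randomly allocate the patients to three sampling groups".

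This is the only stated criterion for the study's main claim, and the possible tests give opposite answers, so choosing among them after seeing the data could reverse the conclusion. Section 5 expects that the results "will have immediate impact on current recommendations for using antigen testing", so an unsupported label of equivalence could carry into practice.

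**Working it through.** **Inputs.** From Section 10: alpha 0.05, power 0.80, 2 df, effect size 0.1, N=964, 10% RT-PCR positive, total N=2000. Hence about 0.10 × 2000 = 200 positives and 1800 negatives. Sensitivity/specificity pairs (Se/Sp below) are assumptions. Pass rates are simulated, 40,000 replicates per scenario.

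**The plan's own figure.** For a chi-square test with effect size w, the noncentrality is N·w². At 2 df (critical value 5.99), power 0.80 needs a noncentrality of 9.635, so N = 9.635/0.1² = 963.5, rounded up to 964. It reproduces. At 1 df the answer would be 785. This is the N for detecting a departure from the null of w=0.1; that 0.1 is not a tolerated difference.

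**(a) Null: no association with RT-PCR (2×2 table, 1 df).** Statistic: N(TP·TN − FP·FN)² / [(TP+FN)(FP+TN)(TP+FP)(FN+TN)]. Take N=1000 with Se/Sp 0.10/0.99, so TP=10, FN=90, FP=9, TN=891:

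1000 × (8910 − 810)² / (100 × 900 × 19 × 981) = 39.1, p = 4×10⁻¹⁰.

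| Se/Sp | Pass, N=964 | Pass, N=2000 |
|---|---|---|
| 1.0/1.0 | 100% | 100% |
| 0.10/0.99 | 99% | about 100% |
| 0.20/0.90 | 79% | 97% |

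A perfect test passes, and so do very poor ones.

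**(b) Null: equality with RT-PCR.** Exact McNemar compares false negatives with false positives, so it responds to their imbalance and not to their number. At N=2000, 0.60/0.99 gives on average 80 false negatives against 18 false positives (p = 1.7×10⁻¹⁰); 0.90/0.99 gives 20 against 18.

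| Se/Sp | McNemar, N=2000 |
|---|---|
| 1.0/1.0 | 0% |
| 0.60/0.99 | 100% |
| 0.80/0.99 | 80% |
| 0.90/0.99 | 4% |
| 0.95/0.99 | 26% |
| 0.60/0.956 | 4% |

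A three-method by result table (2 df, pairing ignored, both antigen tests equally accurate and independent given RT-PCR) runs the same way:

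| Se/Sp | Pass, N=964 | Pass, N=2000 |
|---|---|---|
| 1.0/1.0 | 0% | 0% |
| 0.60/0.99 | 86% | about 100% |
| 0.70/0.99 | 15% | 80% |
| 0.80/0.99 | 0.02% | 0.4% |
| 0.90/0.99 | 0% | 0% |

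In both, p < 0.05 means that the methods differ.

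**(c) Null: sensitivity and specificity both 1.0.** Expected discordant counts are zero, so a single discordant result refutes the null and a perfect test can never give p < 0.05. A test with true sensitivity 0.99 shows at least one false negative among 200 positives with probability 1 − 0.99²⁰⁰ = 0.87. Rejection refutes the plan's own hypothesis.

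**(d) Null: inferior by at least a margin.** This has the right meaning but cannot be run, because no margin is given.

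**The case against.** The strongest reply has five parts.

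- **A hypothesis is stated.** Section 10 does give values of 1.0, so what is missing is, strictly, the designation of a null. This stands as a point of wording but does not help. If 1.0 is the null, p < 0.05 rejects it; if it is the alternative, the complementary null and its margin are absent.
- **McNemar is not named in the plan.** True. The results under (b) apply only if a test of equality is used; they do not forecast what the sponsor would report. Reading (a) is the only runnable one that a good test passes, and it also passes very poor tests.
- **The three-method rates assume conditional independence.** Both antigen tests sample the same person, so this is doubtful. With fully concordant antigen results, 0.60/0.99 at N=964 passes 76% instead of 86%, and 0.70/0.99 at N=2000 passes 69% instead of 80%. The direction is unchanged.
- **Readers would see the estimates anyway.** Section 5 promises that "it will demonstrate weaknesses and strengths of antigen testing", so sensitivity and specificity will probably be reported. But Section 10 does not commit to estimates with confidence intervals, and its only criterion is the p-value.
- **The objective is qualified.** Section 2 refers to symptomatic patients with high viral loads, whereas the Section 10 rule has no such limit. A replacement rule should say which population it covers. If it covers that subset, the positives would be fewer than 200, by a number the documents do not give, and the precision and power figures quoted for the remedy would not apply.

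**Conclusion.** The concern holds, and the rule must be changed before analysis. Under every test that can be run from the text, p < 0.05 either passes antigen tests that miss most infections or can never pass a perfect one. The size depends on the test chosen: 99% of studies would pass Se/Sp 0.10/0.99 under association at N=964; under McNemar at N=2000, 100% would pass 0.60/0.99 but only 4% would pass 0.90/0.99. These figures rest on the plan's 10% positivity and on assumed accuracies. The failure for a perfect test under (b) and (c) needs no such assumption. The 964 is correctly calculated but answers a different question.

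**What to change.** 1. Replace the p-value sentence in Section 10 with: *For each antigen test, sensitivity among RT-PCR positives and specificity among RT-PCR negatives will be reported with exact (Clopper-Pearson) 95% confidence intervals. Acceptable performance is claimed only if both lower limits exceed minimum values fixed before analysis.* State the target population alongside the minimum values. If none are set, report the estimates and intervals and drop the equivalence claim. The value 1.0 may stay as an expectation, not as the tested value.
2. Replace the N=964 chi-square paragraph with the precision, or the joint power for both limits, from about 200 positives and 1800 negatives. For example, 180/200 gives 0.850 to 0.938 and 1782/1800 gives 0.984 to 0.994.

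**Cost.** No participants or procedures are added, but the sponsor must choose minimum values and the stated power may fall below 0.80. With illustrative floors, sensitivity power at 200 positives is 0.97 (true 0.90, floor 0.80), 0.70 (0.95, 0.90) and 0.43 (0.98, 0.95). Specificity power at 1800 negatives is 0.93 (0.99, 0.98) and 0.59 (0.995, 0.99). Joint power per antigen test is the product; values in parentheses are averaged over a binomial number of positives at N=2000:

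| Sensitivity true/floor | Specificity 0.99/0.98 | Specificity 0.995/0.99 |
|---|---|---|
| 0.90/0.80 | 0.91 (0.91) | 0.57 (0.57) |
| 0.95/0.90 | 0.65 (0.66) | 0.41 (0.42) |
| 0.98/0.95 | 0.40 (0.48) | 0.25 (0.31) |

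The last row moves because the exact test is stepwise in the number of positives. Only one of the six combinations reaches 0.80 on either basis. The sponsor should state the joint power, choose attainable floors, or drop the claim. Under the new rule with a floor of 0.80 and 200 positives, a test with true sensitivity 0.60 passes with probability below 0.001.

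### Section 10 wants a verdict on each antigen test, but the only test it names, a two-degree-of-freedom chi-square with no table stated, does not supply one on any of the readings considered

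*Combined protocol and SAP*

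**What the plan says.** The Objective (Section 2) names both products. Section 10 sets the hypothesis for each of them, on two parameters: "We hypothesize that each of the antigen tests has a sensitivity and specificity of 1.0 in relation to RT-PCR". The decision rule is also per product: "A p value of less than 0.05 will be required to consider each of the two rapid tests equivalent to RT-PCR".

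The only test named is the one in the sample-size paragraph of Section 10. It is a chi-square test "for two degrees of freedom, required type I error probability equal to 0.05", with "required (1-type II error probability) equal to 0.8" and a small effect size of 0.1. This gives N=964, described as "observations for consecutive testing of incoming patients in order to fulfill our requirements on significance and power to answer the first research question". The approximation is defended as follows: "Because of the expected number of around 10% positive out of 1000 cases, the assumption of a chi-square distribution is permissible". Enrolment then rises for a different purpose: "To answer this second question, we will extend the study to 2000 participants".

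Section 10 does not say which table or parameters the two degrees of freedom refer to, whether the test is run once or once per brand, or how its p-value becomes a verdict on a brand. It gives no pairwise follow-up and no multiplicity rule. Under Section 8.1 every participant has three swabs, so all three results come from the same person.

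**The concern.** A verdict on one product needs an analysis that speaks about that product alone. One antigen test against RT-PCR, positive or negative by positive or negative, is a 2x2 table with one degree of freedom. Two degrees of freedom arise if RT-PCR, Roche and Abbott are laid out as three rows by two results. The null hypothesis is then that all three have the same positive rate, and there is one p-value for both brands.

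If that is the test, two brands of different quality must receive the same verdict. Taken literally, with p<0.05 meaning equivalent, the worse brand's shortfall would yield an equivalence claim for both. Taken the other way, a brand that agrees perfectly with RT-PCR would fail because of its competitor. Section 5 expects the results to affect recommendations on antigen testing at once, so it matters which brand a conclusion belongs to. Whether p<0.05 can show equivalence at all is a separate question; the present point holds in either direction.

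**Working it through.** **1. The plan's own figure.** Inputs from Section 10: df=2, alpha=0.05, power=0.80, effect size 0.1, taken as Cohen's w because the test is a chi-square. Solve P(noncentral chi-square(2, lambda) > 5.991) = 0.80. This gives lambda=9.635, and N = lambda/w² = 9.635/0.01 = 963.5, rounded up to 964. The figure reproduces, so two degrees of freedom really were used; one would give 785 and three would give 1091. The formula needs only df, w, alpha and power, so N=964 cannot show which table was meant.

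**2. Reading (a): three tests by two results.** Assumptions: 10% RT-PCR positive (Section 10), no false positives, one brand identical to RT-PCR, the other with reduced sensitivity s, and an ordinary unpaired Pearson chi-square on the counts.

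Worked case, 2000 participants and s=0.80:
- Positives: RT-PCR 200, good brand 200, poor brand 160. Total 560 of 6000.
- Expected per row: 560/3 = 186.67 positive and 1813.33 negative.
- Deviations: 13.33, 13.33 and −26.67. Sum of squares 1066.67.
- Chi-square = 1066.67/186.67 + 1066.67/1813.33 = 5.714 + 0.588 = 6.303.
- With 2 df, p = exp(−6.303/2) = 0.043.

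The good brand alone against RT-PCR has p=1.00 and the poor brand alone has p=0.027. The joint test gives 0.043 for both.

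The same calculation with 1000 participants gives joint p=0.21 for 100, 100 and 80 positives, and p=0.026 for 100, 100 and 70.

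Simulation of 100,000 trials per row (RT-PCR positives binomial(N, 0.1), poor-brand positives binomial(RT-PCR positives, s)), share with joint p<0.05:

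| Poor brand's sensitivity | N=1000 | N=2000 |
|---|---|---|
| 0.90 | about 0% | about 0% |
| 0.80 | 4% | 56% |
| 0.70 | 71% | 99.9% |
| 0.60 | 99% | 100% |

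In every one of these trials the good brand matches RT-PCR exactly.

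**3. Reading (b): sensitivity and specificity of one brand tested together.** Two parameters per brand also give two degrees of freedom, with one p-value per brand. The hypothesised values are 1.0 and 1.0. Among D RT-PCR positives the expected number of false negatives is D × (1 − 1.0) = 0; among N − D negatives the expected number of false positives is (N − D) × (1 − 1.0) = 0. Pearson's statistic divides by expected counts, so it is undefined.

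**4. Reading (c): sampling group by result.** The three swab-order groups in Section 8.1 by positive or negative also give two degrees of freedom. That table asks whether swab order matters, not whether an antigen test matches RT-PCR.

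None of the three readings supplies the per-product verdict that Section 10 asks for.

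**The case against.** The strongest objection is that a joint test is nowhere stated. Two degrees of freedom appear only as an input to a power calculation, directly after two sentences that speak of each test separately. A two-parameter hypothesis per brand fits the number 2 as well.

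The plan's own count also fits the three-by-two table poorly. It counts each incoming patient once, whereas stacking three results per patient would turn 964 patients into 3 × 964 = 2892 results, or 964 results into about 321 patients. All of this stands. A reader might infer that the plan pools the brands and that one brand's result decides the other's; the documents do not support stating that as fact. Even on the joint reading, *decides* is too strong. A brand at sensitivity 0.90 almost never moves the joint p below 0.05, and at 0.80 with N=1000 it does so in 4% of trials.

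A reader might also want to replace N=964 with the one-degree-of-freedom sizes, 785 at alpha 0.05 or 951 at alpha 0.025. That does not stand either. On a 2x2 table of antigen result by RT-PCR result, those sizes are for a test of association at w=0.1. They do not size a conclusion about sensitivity and specificity.

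Finally, it can be said that this is only a request for clarification. That goes too far. The per-brand reading does not rescue the plan, because its Pearson statistic cannot be computed under the stated hypothesis. The named test has to be replaced, not merely explained.

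**Conclusion.** The point holds as a mismatch between the decision rule and the named test. Section 10 promises a verdict for each brand on sensitivity and specificity, and the two-degree-of-freedom chi-square gives none on the readings examined.

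The spill-over from one brand to the other depends on the three-by-two reading and on the size of the deficit. At 2000 participants it is 56% of trials at sensitivity 0.80 and 99.9% at 0.70, but about 0% at 0.90. These figures assume 10% RT-PCR positive, no false positives, one perfect brand and an unpaired chi-square. They illustrate what that test would do; they are not error rates of a procedure the plan has specified.

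N=964 is arithmetically correct for a generic two-degree-of-freedom chi-square at w=0.1. It says nothing about the power of the per-product verdicts. The correction should be made before analysis, but it puts neither recruitment nor data collection in doubt.

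**What to change.** In Section 10:

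- Base the verdict on a separate within-patient analysis for each product: a Roche by RT-PCR 2x2 table and an Abbott by RT-PCR 2x2 table, each with sensitivity, specificity, confidence intervals and its own criterion.
- State how multiplicity over the two products is handled.
- Keep any comparison of all three tests descriptive.
- State that N=964 is the size for a generic two-degree-of-freedom chi-square at w=0.1 and does not give the power of the per-product verdicts. Do not substitute 785 or 951.
- Report the expected precision instead. At the plan's 10%, 2000 participants give about 0.10 × 2000 = 200 RT-PCR positives. The approximate 95% half-width for sensitivity is 1.96 × √(s(1 − s)/200): 0.042 at s=0.90, 0.055 at s=0.80 and 0.064 at s=0.70. For an observed sensitivity near 1.0 an exact interval is needed; with 200 of 200 detected, the two-sided 95% lower limit is 0.025^(1/200) = 0.982.

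The cost is wording only, with no further patients, swabs or data. The small downside is that two verdicts are given, so alpha may have to be split between them, which widens each interval somewhat.

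### The 80% power claimed for N=964 belongs to a generic 2-df chi-square test, not to sensitivity, specificity or equivalence with RT-PCR

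*Combined protocol and SAP*

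**What the plan says.** Section 10 makes four statements in sequence.

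- Hypothesis: "We hypothesize that each of the antigen tests has a sensitivity and specificity of 1.0 in relation to RT-PCR".
- Decision rule: "A p value of less than 0.05 will be required to consider each of the two rapid tests equivalent to RT-PCR".
- Sample size: a chi-square power calculation "for two degrees of freedom, required type I error probability equal to 0.05", with power 0.8 and a small effect size of 0.1 in Cohen's sense. From this, "we obtain a number of at least $N=964$ observations for consecutive testing of incoming patients", and the number is said to be chosen "in order to fulfill our requirements on significance and power to answer the first research question".
- Approximation: "Because of the expected number of around 10% positive out of 1000 cases, the assumption of a chi-square distribution is permissible".

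The first research question is never labelled. The only one set out before this point in Section 10 is each antigen test's sensitivity, specificity and equivalence to RT-PCR. That agrees with the objective in Section 2, which is to show performance equal to RT-PCR, at least in symptomatic patients with high viral loads. Section 10 then introduces a second question, on indication groups, and extends enrolment to 2000 for that purpose.

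On design, Section 8.1 states: "Three independent nasopharyngeal swabs will be obtained following standard procedures". To deal with swab order, "we will randomly allocate the patients to three sampling groups".

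**The concern.** A power figure means something only for a stated test of a stated null hypothesis. Section 10 gives a generic effect size and degrees of freedom, but not the table, the null, an equivalence margin or a minimum acceptable sensitivity or specificity. A reader would take 964 as enough to show that the antigen tests match RT-PCR.

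The decision rule matters more than the number. A significant chi-square result shows either association or difference, depending on the table, and neither is equivalence. Section 5 expects the results to influence testing recommendations at once. A rule that could call a poor test equivalent, or read a significant difference as equivalence, is therefore a real risk to the conclusion.

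**Working it through.** **Inputs from Section 10:** 2 df, alpha 0.05, power 0.80, w=0.1, about 10% RT-PCR positive, 2000 participants. **Assumed here:** every sensitivity and specificity below 1.0, independent errors in the simulation, the subgroup sizes and the example minimum values.

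**1. The plan's figure.** Solve P(noncentral χ²(df, λ=N·w²) > χ²(0.95, df)) = 0.80.
- 2 df: critical value 5.991, λ=9.635, N=9.635/0.01=963.5, rounded up to **964** (power 0.8002). It reproduces.
- 1 df: λ=7.849, N=784.9, rounded up to 785.

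**2. What could the 2-df test be?** The plan does not say. These readings are a reconstruction and may not be exhaustive.

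*(a) One antigen test against RT-PCR.* This is a 2×2 table with 1 df, so 964 does not follow. Here w is the phi coefficient:
φ = (Se+Sp−1)·√[π(1−π)/(q(1−q))], with q = π·Se+(1−π)(1−Sp) and π=0.10.
φ=0.1 is reached at Se=0.011 (Sp 1.0) or Se=0.049 (Sp 0.99). So p<0.05 rejects independence even for a nearly useless test.

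*(b) Positive rates across the three tests.* This has 2 df.
- Unpaired, 964 patients × 3 = 2892 results: w=√(9.635/2892)=0.0577. With rates 0.10, q, q and w² = mean((p−p̄)²)/(p̄(1−p̄)), q=0.0671. Both tests then have Se=0.0671/0.10=67% (Sp 1.0), or (0.0671−0.009)/0.10=58% (Sp 0.99). If 964 counts results instead of patients, w=0.1 gives q=0.0477, or about 48% (Sp 1.0).
- Paired (each patient has all three swabs), Cochran's Q, 20,000 simulations of 964 patients at 10% positives:

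| Se / Sp of both antigen tests | Positive rate (RT-PCR 0.100) | Rejected |
|---|---|---|
| 0.90 / 1.0 | 0.090 | 98% |
| 0.90 / 0.99 | 0.1×0.90+0.9×0.01=0.099 | 6% |
| 0.55 / 0.95 | 0.1×0.55+0.9×0.05=0.100 | 5% |

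The last two rows were chosen so that positive rates nearly or exactly match. They show that equal positive rates are compatible with missing 45% of positives. Rejection is evidence of a difference, and non-rejection is not evidence of equivalence.

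*(c) The three sampling-order groups of Section 8.1.* This has 2 df but tests swab order.

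*(d) A joint null of sensitivity and specificity both 1.0,* or a fit to agreement, false negative and false positive. This can be counted as 2 df, but the expected discordant counts under the null are zero, so the chi-square approximation fails.

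**3. The hypothesis of exactly 1.0.** One discordant result refutes it. With 200 positives and a true sensitivity of 0.99, P(at least one false negative) = 1−0.99^200 = 0.866. Perfect agreement does not prove it either: the exact two-sided 95% lower limit is 0.025^(1/200)=0.982 for 200/200 and 0.025^(1/1800)=0.998 for 1800/1800.

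**4. What sensitivity rests on.** Only RT-PCR positives count: 0.10×964≈96, or 0.10×2000=200. Section 10 uses the 10% to defend the approximation, not to derive 964.

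**5. What the study can deliver (Clopper-Pearson 95%).**

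| Observed | Interval |
|---|---|
| 160/200 (80% sensitivity) | 0.738-0.853 |
| 180/200 (90% sensitivity) | 0.850-0.938 |
| 1782/1800 (0.99 specificity) | 0.984-0.994 |
| 45/50 (90%, subgroup with 50 positives) | 0.782-0.967 |
| 90/100 (90%, subgroup with 100 positives) | 0.824-0.951 |

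**The case against.** The strongest reply is that nothing practical depends on 964. The second question sets enrolment at 2000, every participant has both antigen tests and RT-PCR, and sensitivity and specificity with intervals can be computed whatever Section 10 says about chi-square. On that view this is a misattributed power sentence in a single-visit, non-interventional study.

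Part of this stands. The arithmetic is right, and nothing here shows that the study is too small. The 964 sentence alone would be a lesser fault. The reply does not cover the hypothesis of 1.0 or the p<0.05 rule, which form the only stated basis for declaring equivalence and do not support that conclusion under any reading considered.

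A second reply is that the plan may have had another 2-df test in mind, since the readings are reconstructed and the unit of observation is undefined. That is fair. But the joint-null versions fail at the boundary, and changing the unit in (b) moves the implied sensitivity from about 67% to about 48% while leaving a test of difference. It can also be said that the intervals use sensitivities that the plan does not give. They do, and they are illustrations of precision, not predictions.

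**Conclusion.** The concern holds and must be fixed, chiefly because of the equivalence rule. N=964 is correct for a generic 2-df test at w=0.1, but its 80% power does not carry over to sensitivity, specificity or equivalence with RT-PCR. Under the association reading the rule would pass a test with about 1% to 5% sensitivity; under the three-test reading it would treat a significant difference as equivalence. This rests on taking the unlabelled first research question to be the accuracy and equivalence question that precedes it, and on the plan's 10% positivity. The planned 2000 participants are not criticised.

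**What to change.** 1. In Section 10, delete the statement that 964 gives the required power for the first question, and the chi-square justification after it.
2. State instead the exact precision expected from 2000 participants, marking the accuracy values as illustrative: with about 200 positives, 0.738-0.853 at 80% sensitivity and 0.850-0.938 at 90%; with about 1800 negatives, 0.984-0.994 at 0.99 specificity. Say that the counts depend on 10% positivity and that precision is lower in the symptomatic high-viral-load patients named in Section 2.
3. Replace the hypothesis of 1.0 and the p<0.05 rule with each test's sensitivity and specificity and exact 95% confidence intervals.
4. If the objective of demonstrating equal performance is kept, state in advance minimum values, chosen and justified by the sponsor, that the lower limits must exceed. Give exact binomial power over a range of counts, because that power is saw-toothed. Otherwise reword Section 2 as estimation.

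For item 4, with example thresholds only (one-sided 2.5%, each measure taken alone):

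| To show | If the truth is | Count | Power |
|---|---|---|---|
| sensitivity >0.80 | 0.90 | 180-220 positives | 0.954-0.988 |
| sensitivity >0.90 | 0.95 | 180-220 positives | 0.634-0.795 |
| specificity >0.98 | 0.99 | 1780-1820 negatives | 0.926-0.939 |

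Cost: no added patients. The 80% power claim is withdrawn, the hypothesis, decision rule and sample-size paragraph of Section 10 are rewritten, and Section 2 may need rewording. If a decision rule is kept, a demanding minimum may have less than 80% power at about 200 positives, as the second row shows.
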